The Effects of Music and Auditory Beat Stimulation on Anxiety Study Protocol

Approved by the Ryerson Ethics Board: REB 2020-068 on March 26th, 2020, renewal
approval: March 18th, 2021

NCT#:

Date: 2021-11-26

Study Protocol

Participants

Participants (n=318) who are taking anti-anxiety medication will be recruited from Prolific, an online research recruitment platform. A power analysis was conducted drawing effect sizes from a previous study that examined how anxiety levels (measured by the STAI), were affected under the following experimental conditions: binaural beats, music with binaural beats and no-intervention (Padmanabhan et al., 2005). The power analysis indicated that to achieve a power of 0.80 at a significance of $p = 0.05$, a minimum of 45 participants in each treatment group are required (Padmanabhan et al., 2005). An additional 10 participants will be recruited to account for potential participant attrition. Participants will be pre-screened for moderate to severe anxiety using the STICSA trait questionnaire (Grös, Antony, Simms, & McCabe, 2007). Participants will then be randomly assigned to one treatment arm.

Experimental treatment conditions

Each of the experimental treatment conditions below will be 24 minutes in duration, as this seems to be the exposure time needed for binaural beats to reduce anxiety levels and for general effectiveness of binaural beats in other areas such as cognition (Garcia-Argibay, 2019; Isik et al., 2017).

1. Pink noise (control condition)
2. Theta ABS
3. Theta ABS with music generated by LUCID's calm mode
4. Music generated by LUCID's calm mode

Procedure

After reading and signing the consent form and going over experimental expectations, participants will be asked to fill out the Short Test of Music Preferences (STOMP), Queen's Music Questionnaire, the Positive and Negative Affect Scale (PANAS), Self-Assessment Manikin (SAM), Eysenck Personality Questionnaire and the STICSA state version. Participants will then undergo their respective listening condition. After undergoing experimental treatment, participants will complete the following questionnaires: STICSA state version, SAM and the PANAS.

Outcome measures and questionnaires

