**The Effects of Music and Auditory Beat Stimulation on Anxiety
Statistical Analysis Plan**

Approved by the Ryerson Ethics Board: REB 2020-068 on March 26th, 2020, renewal
approval: March 18th, 2021

NCT#:

Date: 2021-11-26

Statistical Analysis Plan

For each participant the post-experimental treatment STICSA, PANAS and SAM Valence and arousal scores will be subtracted from the pre-experimental treatment scores. Shapiro-Wilks normality and homogeneity of variances tests will be done on the STICSA, PANAS and SAM datasets, and homogeneity of covariances tests will be done on music preferences, and personality type datasets to determine if assumptions of the Multivariate Analysis of Covariance (MANCOVA) are satisfied. If these assumptions are satisfied, a MANCOVA over the factor of experimental condition will be performed with music preferences, spontaneous blink rate and personality type as covariates and the relative differences (Pre-treatment – Post-treatment) of STICSA, PANAS and SAM Valence and arousal scores as dependent variables. Post-hoc Tukey's HSD multiple comparisons tests will be done comparing the LUCID music with theta ABS condition with all of the other experimental conditions. Further post-hoc Tukey's HSD multiple comparisons tests will be done comparing the theta ABS and LUCID music conditions with the pink noise condition. Statistically accounting for music preferences, spontaneous blink rate, personality type, age and gender as covariates should reduce some variability in the analysis.

If the data do not satisfy the assumptions for the MANCOVA, permutations tests, specifically the ImPerm package in R will be used to conduct a permutation version of the repeated measures ANCOVA for each dependent variable (STICSA Somatic, STICSA Cognitive, Positive Affect (PANAS), Negative Affect (PANAS) and SAM Valence and arousal scores), with time (pre and post intervention) as the within subjects variable and experimental condition as the between subjects factor. Post-hoc permutation tests will be done comparing the LUCID music with theta binaural beats condition with all of the other experimental conditions for each dependent variable. Permutation tests are a good way to control the type I error rate for multiple comparisons, it is non-parametric and so makes no assumptions about the underlying distribution of the data that are common in other inferential statistical tests (Camargo, Azuaje, Wang, & Zheng, 2008; Good, 1994; Kuehl, 2000).

References

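### The fallback repeated measures ANCOVA does not say how covariates enter; as main effects they cancel from the time-by-condition test, leaving it unadjusted, unlike the MANCOVA it replaces

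*SAP*

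**What the plan says.** The SAP has two branches, chosen by tests of assumptions.

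- **Main branch (SAP, first paragraph).** A MANCOVA across conditions. It takes "the relative differences (Pre-treatment – Post-treatment) of STICSA, PANAS and SAM Valence and arousal scores as dependent variables". The same sentence says that the model is fitted "with music preferences, spontaneous blink rate and personality type as covariates". The paragraph closes with a wider list and a stated purpose: "Statistically accounting for music preferences, spontaneous blink rate, personality type, age and gender as covariates should reduce some variability in the analysis".
- **Fallback branch (SAP, second paragraph).** A "permutation version of the repeated measures ANCOVA for each dependent variable". Six outcomes are listed: two STICSA, two PANAS and two SAM scores. The design is then described in these terms: "with time (pre and post intervention) as the within subjects variable and experimental condition as the between subjects factor". This paragraph gives no covariate list, no covariate-by-time term and no statement of which term tests the treatment.

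The Protocol (Procedure) places the music-preference, music-background and personality questionnaires before the listening session only. Afterwards, "participants will complete the following questionnaires: STICSA state version, SAM and the PANAS". Music preference and personality therefore have one value per person, as do age and gender. Neither document says when spontaneous blink rate is measured.

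**The concern.** The two branches are meant to answer the same question, with the choice between them resting on distributional checks. The first adjusts change scores for covariates directly. The second is called an ANCOVA, which suggests that the same covariates are carried over. In a pre-post repeated measures model, however, a covariate that is fixed over time and entered as a main effect does nothing for the treatment test. A failed normality or variance check would then also switch off covariate adjustment, without the SAP saying so.

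What is at stake is precision, and a like-for-like replacement of the main analysis. The Protocol (Outcome measures and questionnaires) includes music preference because people respond differently to music they prefer. That is an influence on change, which a main effect in this model cannot capture.

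**Working it through.** **1. The plan's own figure.** The Protocol (Participants) says that "to achieve a power of 0.80 at a significance of" 0.05, "a minimum of 45 participants in each treatment group are required". No effect size, SD, test or sidedness is stated, so 45 can only be solved backwards:

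- Two means, two-sided 0.05, normal approximation: d = (1.960 + 0.842) × √(2/45) = 0.59.
- Four-arm one-way ANOVA with f = 0.25 (assumed): noncentrality 0.25² × 180 = 11.25 on (3, 176) df gives power 0.804, and 45 is the smallest group size that reaches 0.80.

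The documents give no figure for the fallback's power or for the variance that covariates explain.

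**2. The algebra.** For person i at time t (0 = pre, 1 = post), in condition c, with fixed covariate x:

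Y(i,t) = s(i) + βx(i) + [τ + γ(c)]t + e(i,t)

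Subtracting post from pre gives D(i) = −[τ + γ(c)] + error. Both s(i) and βx(i) cancel. The time-by-condition test is therefore the one-way ANOVA on D, with or without x. Adding a term δx(i)t makes D(i) = −[τ + γ(c)] − δx(i) + error, which is the change-score ANCOVA.

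**3. Numerical check.** One simulated data set (4 arms × 45, pre and post, one fixed covariate related to change), fitted by least squares with subject effects:

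| Specification | Time-by-condition F | df |
|---|---|---|
| No covariate | 5.058 | 3, 176 |
| Covariate main effect only | 5.058 | 3, 176 |
| Main effect plus covariate-by-time | 6.997 | 3, 175 |

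The first two equal the ANOVA on change: (10.176/3)/(118.029/176) = 5.058. The third equals the ANCOVA on change: (10.475/3)/(87.333/175) = 6.997.

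**4. Possible loss of power.** Inputs: N = 318 (Protocol, Participants). Assumed: arms of 80, 80, 79 and 79; one arm of 80 shifted by d SDs of change; omnibus 3-df test at 0.05; 5 covariate degrees of freedom; covariates explaining a share R² of within-arm change variance. Then

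λ = d² × (80 × 238/318)/(1 − R²) = 59.87 d²/(1 − R²)

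and power is the upper tail of the noncentral F on (3, 314) df unadjusted or (3, 309) df adjusted. For d = 0.4, λ is 9.58 unadjusted and 9.58/0.70 = 13.69 at R² = 0.30.

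| Shift d | Unadjusted, or main effects only | R² 0.05 | R² 0.10 | R² 0.20 | R² 0.30 |
|---|---|---|---|---|---|
| 0.4 | 0.735 | 0.759 | 0.784 | 0.834 | 0.884 |
| 0.5 | 0.913 | 0.927 | 0.940 | 0.964 | 0.981 |
| 0.59 | 0.979 | 0.984 | 0.988 | 0.994 | 0.998 |

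The loss at d = 0.4 runs from 0.759 − 0.735 = 0.024 to 0.884 − 0.735 = 0.149. At d = 0.59 it is at most 0.998 − 0.979 = 0.019. At R² = 0 it is nil.

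**The case against.** The strongest reply is that the SAP is silent rather than wrong. The fallback paragraph neither includes nor excludes covariate-by-time terms, and with them the test is exactly the change-score ANCOVA. This stands. The point is conditional on covariates entering as main effects, a specification that the text permits but does not state.

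A reader might infer that the SAP's statement about reducing variability is untrue in the fallback. The documents do not support that. The sentence closes the MANCOVA paragraph, where covariates act directly on change and the cautious wording is reasonable, and the fallback paragraph does not repeat it.

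A reader might also infer that every listed covariate cancels. That cannot be shown for blink rate, because a measure taken both before and after would not cancel.

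Finally, the power figures rest on assumed effects and assumed R². At the effect implied by the Protocol's 45 per group (itself a back-calculation, applied here to the SD of change), N = 318 leaves little to lose. This also stands, and it limits the size of the point. It does not remove the mismatch between branches.

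**Conclusion.** The fallback is under-specified. If the pre-treatment covariates enter as main effects, which is a natural reading of a repeated measures ANCOVA described only by time and condition, its treatment test is an unadjusted comparison of change scores and does not match the adjusted MANCOVA.

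Randomised assignment keeps that comparison valid, so a reader should not infer bias or an inflated type I error. Nor is a loss of power certain. It depends on how well the covariates predict change and on the true effect, neither of which the documents give. Within the assumed ranges it goes from negligible to about 15 points. The algebra is exact; the size is not known. The amendment is worth making because it is nearly free.

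**What to change.** Replace the fallback model with a permutation ANCOVA that has one record per participant. For each outcome, regress the post score on condition, with that outcome's baseline score and the main model's pre-treatment covariates, and permute the condition labels. Write out the covariate list once for both branches. That means settling whether age and gender belong in it (they are in the closing sentence but not in the model sentence) and when blink rate is measured.

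The MANCOVA has no baseline score among its covariates at present. Add the same baseline adjustment there, or the branches will still differ. A MANCOVA applies one covariate set to all outcomes, so the baseline scores would enter together; for an exact match, use that set in both branches.

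If the repeated measures form is kept, add a covariate-by-time term for each covariate and name time-by-condition as the test of treatment.

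The cost is a few sentences in the SAP and slightly different code, with no new data beyond those already planned. With four arms and 5 covariate degrees of freedom (assumed), 318 − 4 − 5 = 309 error degrees of freedom remain; the six baseline scores together would leave 303.

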Participants show a more pleasurable emotional response to their own preferred music compared to experimenter-selected music (Davis & Thaut, 1989; Thaut & Davis, 1993). We therefore decided to incorporate the Short Test of Music Preferences (STOMP) as a covariate in our analyses (Rentfrow & Gosling, 2003). The Queen's Music Questionnaire will be administered to assess musical education and daily music exposure of each participant, which will be used as a covariate in our analyses. The Eysenck Personality Questionnaire will be used to determine participants' extraversion and introversion (Rocklin & Revelle, 1981). The State Trait Inventory for Cognitive and Somatic Anxiety (STICSA) will be used to pre-screen high trait anxiety participants (trait version) for participation in this study (Grös et al., 2007).

The state version of STICSA will be used to assess state anxiety before and after experimental treatment. This will serve as the primary outcome measure. The Positive and Negative Affect Scale (PANAS) will be used to assess mood (Watson, Clark, & Tellegen, 1988) before and after experimental treatment. The Self-Assessment Manikin (SAM)

questionnaire will be used to assess valence and arousal of the participant before and after experimental treatment (Bradley & Lang, 1994).

References

Bradley, M. M., & Lang, P. J. (1994). Measuring emotion: The self-assessment manikin and the semantic differential. *Journal of Behavior Therapy and Experimental Psychiatry*, 25(1), 49-59. doi:[https://doi.org/10.1016/0005-7916\(94\)90063-9](https://doi.org/10.1016/0005-7916(94)90063-9)

Davis, W. B., & Thaut, M. H. (1989). The Influence of Preferred Relaxing Music on Measures of State Anxiety, Relaxation, and Physiological Responses. *Journal of Music Therapy*, 26(4), 168-187. doi:10.1093/jmt/26.4.168

Garcia-Argibay, M. (2019). Efficacy of binaural auditory beats in cognition, anxiety, and pain perception: a meta-analysis. *Psychological Research*, 83(2), 357-372. doi:10.1007/s00426-018-1066-8

Grös, D. F., Antony, M. M., Simms, L. J., & McCabe, R. E. (2007). Psychometric properties of the State-Trait Inventory for Cognitive and Somatic Anxiety (STICSA): Comparison to the State-Trait Anxiety Inventory (STAI). *Psychological assessment*, 19(4), 369.

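### The permutation fallback relies on permutation testing to control multiplicity, but names no adjustment, family or omnibus gate for its separate post-hoc tests

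*SAP*

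**What the plan says.** The SAP has two analysis paths.

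- **Main path (SAP, first paragraph).** After the MANCOVA: "Post-hoc Tukey's HSD multiple comparisons tests will be done comparing the LUCID music with theta ABS condition with all of the other experimental conditions". Then: "Further post-hoc Tukey's HSD multiple comparisons tests will be done comparing the theta ABS and LUCID music conditions with the pink noise condition". That is five of the six possible pairs of arms, with a named adjustment.
- **Fallback (SAP, second paragraph).** "If the data do not satisfy the assumptions for the MANCOVA, permutations tests, specifically the ImPerm package in R will be used". A permutation repeated-measures ANCOVA is run for each of six variables: "STICSA Somatic, STICSA Cognitive, Positive Affect (PANAS), Negative Affect (PANAS) and SAM Valence and arousal scores". Then: "Post-hoc permutation tests will be done comparing the LUCID music with theta binaural beats condition with all of the other experimental conditions", again for each variable. Theta ABS versus pink noise and LUCID music versus pink noise are not listed here.

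On multiplicity in the fallback, the SAP says only: "Permutation tests are a good way to control the type I error rate for multiple comparisons". It cites three works, one of them titled on multiple hypotheses. It does not name an adjustment or a family of tests, and it does not say whether the pairwise tests wait for a significant overall test.

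The protocol (Outcome measures and questionnaires) says of STICSA state: "This will serve as the primary outcome measure". The fallback analyses it as two subscales.

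**The concern.** The quoted sentence treats a property of some permutation procedures as if every permutation test had it. A permutation p-value is valid for its own test. Error over a set of tests is controlled only if the set is handled jointly, for example by permuting the largest statistic, or if the p-values are adjusted afterwards. Naming an R package and a reference does not settle which is meant.

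An analyst following the paragraph literally would report unadjusted pairwise p-values and believe them to be controlled. The same comparison would then be protected by Tukey on one path and possibly unprotected on the other, with the assumption tests deciding which path applies. The comparisons most exposed are those of the combination with its two components, because an omnibus test can be significant through pink noise alone.

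**Working it through.** **Inputs.** There are four arms and 318 participants (Protocol, Participants: "Participants (n=318) who are taking anti-anxiety medication will be recruited from Prolific"). The allocation ratio is not stated; with equal arms, 318/4 = 79.5, taken as 79. The level 0.05 appears only in the power statement. Two-sided testing, change scores without covariates, and a correlation of 0 to 0.9 between the STICSA subscales are assumptions. The documents state no family-wise rate for either path, so there is no figure of the plan's own to reproduce.

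**Count.** Main path: 3 + 2 = 5 comparisons. Fallback: 3 comparisons per variable, with 2 of the five unlisted.

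**One outcome, no effect.** Three independent tests would give 1 − 0.95³ = 0.143. The three share the combination arm, so they are correlated and the rate is lower: 0.126 by simulation of the joint normal distribution. If the tests follow only a significant omnibus test, the rate is 0.039–0.040. Five Tukey comparisons give 0.043–0.044.

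**Two STICSA subscales, no effect.** With uncorrelated subscales the ungated rate is 1 − (1 − 0.126)² = 0.236, and correlation lowers it. Simulated over correlations 0 to 0.9:

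| Rule | Chance of at least one false positive |
|---|---|
| Fallback, ungated | 0.18–0.23 |
| Fallback, each subscale gated by its own omnibus test | 0.06–0.08 |
| Tukey, if the main path also used subscales | 0.06–0.09 |

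At 45 per arm the no-effect results are within 0.01 of these.

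**Permutation p-values rather than t-tests.** With skewed (exponential) data, 79 per arm and 999 permutations, a single test rejects at 0.048–0.051, as it should. Within one outcome the three ungated tests give 0.120–0.128, and over two subscales 0.178–0.229. In a separate run with skewed data, 45 per arm and 1,500 trials, separate tests gave 0.14 and a max-statistic over the same three gave 0.059 (simulation standard errors 0.009 and 0.006). So permutation alone does not control the set, while a joint permutation statistic does so within simulation error.

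**Active arms equal, all better than pink noise.** Two of the three null hypotheses are then true, and the gate opens because of pink noise. At 0.5 SD, 79 per arm, gated:

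| Error event | Per outcome | Over two subscales |
|---|---|---|
| Combination differs from either component, either direction | 0.09 | 0.13–0.17 |
| Combination favoured over at least one component | 0.04 | 0.06–0.09 |
| Combination favoured over both components | under 0.01 | under 0.01 |
| Tukey, either component, either direction | 0.02 | 0.03–0.04 |

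The first row depends on the difference from pink noise. Per outcome it is 0.05 at 0.2 SD with 45 per arm, 0.06 at 0.3 SD with 45 per arm, and 0.09 at 0.8 SD with 79 per arm.

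**Power cost of an adjustment.** For a comparison with 0.80 power at two-sided 0.05, the expected statistic is 1.960 + 0.842 = 2.802. The critical value of the maximum of five comparisons is about 2.52, so power is Φ(2.802 − 2.517) = Φ(0.285) = 0.61. For Tukey with four arms (2.569) it is Φ(0.233) = 0.59. For the three comparisons now listed (2.350) it is Φ(0.452) = 0.67.

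**The case against.** Four points can fairly be made against this.

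1. **The ungated rates are the least favourable reading.** The pairwise tests are called post-hoc and come after an overall test for each variable, which suggests a gate. The SAP also states an aim of controlling error and cites a work on multiple hypotheses. This stands in part: a reader might infer that 0.18–0.23 is the plan's error rate, but the documents do not say the tests run ungated. They do not say the tests are gated either. With a gate and no effect, the fallback is no worse than Tukey.

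2. **The 0.13–0.17 figure is not the error rate of a claim that combining adds something.** It counts a difference from either component, in either direction, so it includes the combination looking worse. If the claim requires beating both components, the chance is under 0.01 and no adjustment across those two comparisons is needed. The SAP states no such rule, but a reader should not take 0.17 as the risk of a false claim of benefit. This stands fully.

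3. **Multiplicity over subscales and over all outcomes is not specific to the fallback.** This also stands. The main path leaves it open too, and its paragraph names STICSA without subscales. An error rate over all six variables cannot be charged to the permutation path.

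4. **The shorter list of comparisons may be deliberate.** The documents give no reason for it. The mismatch is a matter of consistency and does not itself inflate error.

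What remains is that the plan relies on a property its separate tests do not have. That is more than missing detail.

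**Conclusion.** The concern holds in this limited form: on the permutation path, control of error across the post-hoc comparisons rests on a statement that is not true of separate permutation tests, and no adjustment, family or gate is given. Whether the error rate within one outcome is about 0.13 or 0.04 depends on a choice the SAP leaves open. Even with a gate, when the active arms are equally effective, the combination-versus-component comparisons carry a rate of about 0.09 per outcome for any false difference, where Tukey gives 0.02.

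The sizes rest on the assumptions listed with the working. How likely the fallback is to be used cannot be told from the documents. This should be fixed before analysis. It does not show that the fallback's results would be wrong, or that the fallback is worse than the main path in every case.

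**What to change.** Replace the quoted sentence with a named procedure. One possible wording: *Within each dependent variable, the five pairwise comparisons listed for the MANCOVA path are tested on change scores with a max-statistic (or step-down) permutation adjustment at two-sided family-wise 0.05.* Holm on the pairwise permutation p-values is an alternative; its first step over five comparisons is 0.05/5 = 0.01. Also:

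- State whether post-hoc tests require a significant omnibus test. With the adjustment in place, a gate is not needed for error control within an outcome.
- List the same comparisons on both paths, or say why the fallback has fewer. Make this change together with the adjustment, because two further unadjusted comparisons would raise the ungated one-outcome rate from 0.126 to 0.183.
- Fix the test statistic and the number of permutations in advance. With B permutations the smallest attainable p-value is 1/(B + 1), so a first Holm step of 0.01 needs at least 99.
- Settle separately, for both paths, how the two STICSA subscales serve one primary outcome and how the remaining outcomes are treated.

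The cost is SAP wording and a few lines of code, with no new data. The downside is power: a comparison with 0.80 unadjusted falls to about 0.6 with five comparisons in one outcome, about what Tukey already costs on the main path.

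### The permutation fallback neither controls error over its three post-hoc contrasts nor escapes the equal-variance condition as written; both can be fixed with a studentised max-T test.

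*SAP*

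**What the plan says.** All of this is in the SAP's Statistical Analysis Plan section.

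- **Checks (first paragraph).** "Shapiro-Wilks normality and homogeneity of variances tests will be done on the STICSA, PANAS and SAM datasets". So unequal variance is one of the conditions that can rule out the MANCOVA. In the MANCOVA branch the pairwise comparisons use Tukey's HSD.
- **Fallback (second paragraph).** "If the data do not satisfy the assumptions for the MANCOVA, permutations tests, specifically the ImPerm package in R will be used". The overall test is a permutation analogue of a repeated measures ANCOVA, run separately on six listed outcomes, with time as the within-subject factor and condition as the between-subject factor.
- **Contrasts in the fallback.** "Post-hoc permutation tests will be done comparing the LUCID music with theta binaural beats condition with all of the other experimental conditions", which makes three contrasts per outcome.
- **Justification.** The first reason given is "Permutation tests are a good way to control the type I error rate for multiple comparisons". The second reason, about the method's assumptions, is "it is non-parametric and so makes no assumptions about the underlying distribution of the data". A closing qualifier limits this second reason to assumptions shared by other tests.

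The SAP does not give the permutation statistic, whether it is studentised, whether a contrast shuffles two arms or all four, an adjustment over the three contrasts, or a rule that a contrast is read only after a significant overall test. The Protocol (Participants) gives 318 participants, a 0.05 significance level and random assignment to one arm, with no allocation ratio.

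**The concern.** The justification rests on two properties that permutation does not supply by itself.

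**Multiplicity.** Permutation controls error over a family of contrasts only if a joint statistic is permuted, for example the maximum over the contrasts. Three separate permutation tests, each at 5%, behave like any three unadjusted tests. The fallback therefore offers less protection than the Tukey comparisons it replaces, while claiming to control this error.

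**Variance.** As a test of equal means, an ordinary mean-difference or ANCOVA-type statistic has the right size only if observations are exchangeable between arms under the null. Unequal variances break that. Equal variance is one of the assumptions common to other tests, and its failure is one of the events that lead here.

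At stake are the comparisons of the music-plus-theta arm with each other arm, which carry the trial's main conclusions.

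**Working it through.** **Inputs.** From the documents: 318 participants, four arms, alpha 0.05 (two-sided assumed), three fallback contrasts. Assumed, because the documents do not give them: arm sizes (80/80/79/79, and 84/84/85/65 with the combination arm at 65), combination-arm SD 1, 1.5 or 2 times the others, normal change scores with equal means, no covariates. With two time points, the time-by-condition test is a one-way test on change. The plan gives no error rate for the fallback, so there is no figure of its own to reproduce.

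**Step 1: three unadjusted contrasts.** If independent, the chance of any false positive would be 1 − 0.95³ = 14.3%. The contrasts share the combination arm, so at equal n their correlation is s²/(s² + 1), where s is the SD ratio: 0.50, 0.69 and 0.80 for s = 1, 1.5 and 2. For three equicorrelated normal statistics, each tested at |z| > 1.96, the chance of any rejection is then 12.5%, 11.0% and 9.8%.

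**Step 2: size of one contrast in large samples.** The true variance of the mean difference is T = s₁²/n₁ + s₂²/n₂. The variance P implied by shuffling is:

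- two compared arms only: P = s₁²/n₂ + s₂²/n₁
- all four arms: P = v(1/n₁ + 1/n₂), with v the n-weighted mean variance

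Actual size = 2[1 − Φ(1.96√(P/T))].

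- Two arms, equal n: P = T, so 5.0% at any SD ratio.
- Two arms, 65 v 84, s = 1.5: T = 0.0465, P = 0.0422, size 6.2%.
- Two arms, 65 v 84, s = 2: T = 4/65 + 1/84 = 0.0734, P = 4/84 + 1/65 = 0.0630, P/T = 0.858, size 6.9%.
- Two arms, 105 v 71, s = 2 in the larger arm: T = 0.0522, P = 0.0659, size 2.8%.
- All four arms, equal n, s = 1.5: v = 5.25/4 = 1.3125, P/T = 2.625/3.25 = 0.808, size 7.8%.
- All four arms, equal n, s = 2: v = 7/4 = 1.75, P/T = 3.5/5 = 0.70, size 10.1%.
- All four arms, combination arm 65, s = 2: v = (253 + 65 × 4)/318 = 1.613, P = 0.0440, P/T = 0.599, size 12.9%.

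**Step 3: simulation** (4,000 null trials × 399 permutations; standard error about 0.35 points per contrast). Entries are for SD ratio 1 / 1.5 / 2.

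| Version | 80/80/79/79 | 84/84/85/65 |
|---|---|---|
| Two arms shuffled, per contrast | 5.1 / 5.2 / 5.3% | 4.8 / 6.0 / 6.9% |
| Two arms shuffled, any of three | 12.8 / 11.4 / 10.2% | 11.8 / 12.6 / 12.8% |
| All arms shuffled, per contrast | 5.1 / 8.0 / 10.6% | 4.6 / 9.0 / 13.0% |
| All arms shuffled, any of three | 12.7 / 17.3 / 19.8% | 11.5 / 18.1 / 22.9% |
| Welch-studentised, per contrast | 5.1 / 5.1 / 5.2% | 4.7 / 4.6 / 4.8% |
| Studentised max-T, any of three | 5.2 / 4.6 / 4.3% | 4.5 / 3.9 / 3.6% |

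**Step 4: overall test and reverse case** (15,000 trials × 499 permutations; standard error 0.2 to 0.3 points). The unstudentised four-arm test has size 4.8%, 5.5% and 6.5% at SD ratios 1, 1.5 and 2 with near-equal arms. With SD ratio 2 in the largest arm (105/71/71/71) it is 3.7%. The contrast there is 2.8% with two-arm shuffling and 6.4% with all-arm shuffling.

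**The case against.** The strongest reply is that the SAP is silent rather than wrong, and that the larger error rates need choices it never makes. Much of this stands.

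- A reader might infer that the SAP has chosen an unstudentised statistic with labels shuffled over all arms, so that a failed variance check automatically inflates error. The documents do not support this. An ordinary ANCOVA-type statistic is the natural reading for the overall test, but nothing is named for the contrasts, and comparing one condition with another reads at least as naturally as two-arm shuffling. On that reading, at equal n, unequal variance causes no inflation.
- A reader might infer that the SAP claims a test free of all assumptions. It does not: the sentence is limited to assumptions common in other tests. It still misleads, because equal variance is one of those.
- A reader might infer that a mix of responders and non-responders in the combination arm would give false positives. Such a mix normally shifts the mean, so rejection would not be an error.
- Under random assignment the permutation test is valid for the strict null of no effect on anyone. It is also appropriate where only normality fails and spreads are equal.
- If post-hoc means that contrasts are read only after a significant overall test, any-false-positive error under the complete null falls to 5.0%, 5.7% and 6.3% at near-equal arms for SD ratios 1, 1.5 and 2, even with all-arm shuffling. At 84/84/85/65 it is 6.4% and 8.8% for ratios 1.5 and 2. But no such gate is stated, and it protects only when all arms are equal. If one arm truly differs, the remaining contrasts are again unadjusted.
- The SAP cites a source on permutation tests for multiple hypotheses, so an adjustment may be intended. None is specified.

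These points limit the variance part. They do not remove the multiplicity part, which needs no assumption about variances or shuffling.

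**Conclusion.** The point holds in two parts of unequal strength.

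**Multiplicity is the firmer part.** Without a stated gate or joint adjustment, the three fallback contrasts carry about a 10% to 13% chance of any false positive within one outcome, whatever the variances, and more if labels are shuffled over all arms and variances differ.

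**The variance part is conditional.** At assumed SD ratios of 1.5 to 2 in the combination arm, per-contrast error is about 5% with two-arm shuffling at equal n, 6% to 7% with two-arm shuffling when that arm is smaller (65 v 84), and 8% to 13% with all-arm shuffling. When the more variable arm is the larger one, two-arm shuffling is conservative; all-arm shuffling was still slightly above 5% in the case examined. The plan does not exclude the unfavourable cases, because it fixes neither the statistic, the scheme nor the allocation ratio.

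These figures rest on normal change scores, no covariates and assumed SD ratios and arm sizes. They concern the null of equal means. The change should be made before the analysis; it is not evidence that any result would be wrong.

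**What to change.** In the fallback:

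1. Use a Welch-type studentised statistic for each planned contrast.
2. Shuffle the condition labels jointly and compare each contrast with the permutation distribution of the largest absolute statistic over the planned contrasts (single-step max-T), separately within each outcome.
3. State the statistic, the shuffling scheme and how covariates enter.
4. Replace the justification sentence with one saying that the test relies on exchangeability, that studentising protects the comparison of means when variances differ, and that max-T gives the control over the contrasts.

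In the settings simulated this held per-contrast error at 4.6% to 5.2% before the max-T step, and error over the three contrasts at 3.6% to 5.2% with it. It does not adjust across the six listed outcomes.

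Cost: a few lines of R in place of the package default, one revised SAP paragraph, and slightly less power than unadjusted contrasts. No change to recruitment or data collection.
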